9.5 Study Size

All analyses (except the estimation of the prevalence of NVAF) will be conducted in patients newly diagnosed with FA. In 2018, a study conducted by Santé Publique France, showed that 225,747 NVAF patients were OAC new users (6). If the number of new patients remains constant during the study period of 5 years from 2016 to 2020, we expect that approximately 1.3 million patients will be exposed to OAC in the SIFNOS study.

9.6 Data Management Plan

Data management for this study will be conducted using standard IQVIA processes. Further details on the data handling procedures are provided below. The process would take into consideration any data governance imposed on the data source including any plans to handle the data outside of the institution or country of origin. IQVIA will adhere to all local and regional laws on data protection and privacy.

Data transfers

Trained IQVIA personnel involved in the study and specified in the contract with CNAM will get access to the SNDS secure web portal where the extracted data will be made available. They will receive an email containing their login dedicated to this study and a mail, delivered by a carrier against signature, containing a token dedicated to this study too. The token will first be activated via the IQVIA internal activation code provided by CNAM to IQVIA for all the studies conducted on SNDS. Then, the owner will define his/her own activation code to be able to generate a random 8-digit password valid for one minute and allowing the connection to the secure SNDS web portal.

Trained IQVIA personnel involved in the study will access the data via secure IQVIA computers and internet connections and will perform the data management and the analysis through the secure SNDS web portal. As specified in the contract with CNAM, they are banned from downloading individual patient data from this portal to a local computer (i.e., no transfer of data will take place from CNAM to IQVIA) as well as displaying or reproducing these data in any format (e.g., Excel®, screen shot) and for any purpose (e.g., data review). No technical solutions are implemented for ensuring these requirements. Trained IQVIA personnel involved in the study are personally accountable to the French law to comply with these conditions.

Data storage and backup

Extracted data will be stored on CNAM's servers in a dedicated data folder accessible only to trained IQVIA personnel involved in the study. Each CNAM's server systematically contains a copy of the study data folder with all extracted and derived data tables as a backup copy.

Data cleaning and preparation

Extracted data are made available in the form of several hundreds of tables and several thousands of variables. The overall aim of data cleaning and preparation is to clean and to gather the data within a reduced work-frame.

Details of the process is available upon request.

Data analysis and results generation

The same trained IQVIA statistician will create the derived variables and will perform data analysis following the instructions provided in the signed-off statistical analysis plan. It will also develop dedicated macros to report the results within the format specified in the table shells in the signed-off statistical analysis plan automatically in a Microsoft Word® document.

Data archival/destruction for project close

The study data folder including all extracted and derived data tables will be destroyed from all the CNAM's servers at the end of the official communication of the results of this study, as clarified in the submitted ethics dossier. No archive of the study data folder can be requested.

Quality control (QC) processes

At the end of each of the following key stages – data management of the extracted data, derived variables creation, data analysis and results reporting – the Statistical Analysis Software (SAS) programs used will be inspected and quality checked by a second trained IQVIA statistician involved in the study and different from the one who will perform the stages. Validation of the SAS programs and successful execution of QC after each stage will be necessary in order to proceed to the following stage.

Data management risks

As data will not be transferred to IQVIA and only trained personnel will be able to access it for the purpose of analysis and results generation, there is no foreseeable risk that is expected to affect data integrity or data protection.

9.7 Data Analysis

9.7.1 General Considerations

Individual patient data will be analysed through the SNDS secure web portal using SAS Enterprise Guide® version 7.1. Aggregated data will be exported to an IQVIA secure server to generate figures of results using R version 3.6 or higher, or SAS® version 9.4 (SAS Institute North Carolina, USA).

Results will be reported only if they represent at least 10 patients to comply with French individual data protection policy. In the event of subgroups include strictly less than 10 patients, the analysis will not be performed, or the subgroups will be re-defined to extend the populations to be included. Decision will be taken on a case-by-case basis in agreement with PFIZER/BMS, IQVIA and/or the experts of the scientific committee.

Presence of missing data is not expected in SNDS because of its completeness. Therefore, results will not report missing data and no imputation of missing data will be done.

Descriptive analysis will be conducted depending on the nature of the variable:

- For qualitative variables, this includes the number of observed (and missing if relevant) values, and the number and percentage of patients per class. Percentages will be calculated in the population without missing data.
- For quantitative variables, this includes number of observed (and missing if relevant) values, mean, standard-deviation, median, first and third quartiles, and minimum and maximum.

An overview of the planned analysis for the primary, secondary and exploratory objectives is presented in **Error! Reference source not found..**

Table XXI. Overview of the data analysis by objective

Type of Objective	Primary	Secondary					Exploratory	
Name of the analysis	To estimate the incidence rate of stroke (ischemic or hemorrhagic), major bleeding and death in both AF patients (exposed and unexposed to OAC)	To describe the characteristics of AF patients exposed and unexposed to OAC	To compare the incidence rate of stroke, major bleeding, and death between those two populations	To estimate the annual incidence and prevalence of patients with AF, exposed and unexposed to OAC	To describe the use of oral anticoagulants (OACs) in AF patients initiating treatment (AF patients exposed to OAC therapy)	To compare the Healthcare Resource Utilization (HCRU) and associated costs between patients exposed to apixaban, rivaroxaban, dabigatran, VKA and patients unexposed to OACs	To describe the therapeutic management before/after the first stroke occurring after initiation of OAC exposure	To identify subgroups among AF patients with similar profile
Outcomes	Estimation of the incidence rate of stroke, major bleeding, and death. Incidence rate in unexposed patients will be standardized on age using the exposed to OAC group as population of reference.	Description of sociodemographic characteristics, comorbidities, medical history of interest and concomitant treatments	Comparison of incidence rate in longitudinal analysis for each event of interest (stroke, major bleeding, and death)	Estimation of the annual incidence and prevalence of patients with AF. Annual incidence will be standardized on age using INSEE data (French population) as population of reference	Description of the use of oral anticoagulants (OACs) in AF patients initiating treatment (AF patients exposed to OAC therapy)	Comparison of the Healthcare Resource Utilization (HCRU) and associated costs between patients exposed to apixaban, rivaroxaban, dabigatran, VKA and patients unexposed to OACs	Description of the therapeutic management before/after the first stroke occurring after initiation of OAC exposure	Identification of subgroup of AF patients with similar profile

Periods	2016 - 2019	2016-2019 (per calendar year)	2016 - 2019	2014 – 2019 (per calendar year)	2016 - 2019	2016 - 2019	2016 - 2019	2016 - 2019
Populations	Incident AF patients	Incident AF patients	Incident AF patient	All AF patients (prevalent & incident)	Incident AF patients exposed to OAC	Incident AF patients exposed and unexposed to OAC	Incident AF patients exposed to OAC	Incident AF patients exposed and unexposed to OAC
Subgroups	Elderly patients (\geq 80 years old) Patients with CAD Frail patients Patients having an active cancer Patients reported with previous stroke		-Patients with high thromboembolic risk	Elderly patients (\geq 80 years old) Patients with CAD Frail patients Patients having an active cancer Patients reported with previous stroke				
Stratification	-Modified CHAD ₂ DS ₂ VASC score strata (Low risk / Moderate risk/ High risk) - For stroke event type of stroke (ischemic or hemorrhagic)							

Type of analysis	Longitudinal	Cross-sectional	Longitudinal	Cross-sectional	Longitudinal	Longitudinal	Longitudinal	Longitudinal
Analysis methods	Descriptive	Descriptive	Cox regression model with OAC exposure considered as time-dependent variable (Crude and variable described in table XV)	Descriptive	Descriptive	Descriptive + ANOVA or Welch test or Kruskal-Wallis (according to the verification of the hypothesis) + post-hoc test (if previous global test significant)		Clustering models (TAK, K-Means, Random-Forest, Ascending hierarchical clustering) with a data visualization
Sensitivity analyses	
 -Integration of 2020 data -30 and 90 days of maximal number of days allowed for being refilled -Integration of all incident AF patients (i.e. inclusion of patients with an event of interest between inclusion date and index date) 	
 -Integration of 2020 data 	
 -Integration of 2020 data -30 and 90 days of maximal number of days allowed for being refilled 
 - Integration of all incident AF patients (i.e. inclusion of patients with an event of interest between inclusion date and index date) 	
 -Integration of 2020 data -Integration of all incident AF patients (i.e. inclusion of patients with an event of interest between inclusion date and index date) 
 - On AF patients identified only by LTD or hospitalization (new OAC users identified) 				

				by algorithm of Billionnet et al. not included)				
--	--	--	--	---	--	--	--	--

9.7.2 Planned Analysis for the Selection of the Study Population

The selection of the study population will be described as counts of patients included or excluded after each inclusion or exclusion criterion and after the algorithm and summarized through a flow diagram.

Description of the duration of the follow-up in years and the reason for end of follow-up (death, lost to follow-up or end of the study period) will also be provided for AF patients exposed and unexposed to OAC and overall.

9.7.3 Planned Analysis for the Primary Objective

9.7.3.1 To estimate the incidence rate of stroke (ischemic or hemorrhagic), major bleeding and death in AF patients exposed to OAC (VKA or DOAC) and unexposed to OAC

The analysis of incidence rate for the first occurrence of each event of interest (stroke, major bleeding and death) will be conducted in the population of AF incident patients excluding those with a reported outcomes of interest up to 30 days prior index date.

As a reminder, incident AF patients will be the patients newly diagnosed AF during the inclusion period i.e., with a date of first diagnosis of AF, identified by the date of the start of LTD or of the index hospital stay during inclusion period, or the date of initiation of the OAC.

Event rates will be estimated over the 4-year period 2016-2019, in the overall population and according to the treatment exposure.

The incidence rate for each event of interest (stroke, major bleeding and death) will be defined as the number of events occurring during the follow-up period divided by the number of person-years of follow-up (sum of durations of follow-up period for incident patients).

Incidence rates in unexposed patients will be standardized by age using exposed patients as the population of reference.

Analyses will be descriptive in nature (proportion and 95% confidence interval).

Event rates will also be displayed by sub-populations (see section [9.2.3.4](#)).

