9.2.1.4 Follow-up and Censoring

[figure not shown]
The Follow-up period starts at index date and ends on the date of occurrence of one of the following events:

- Death;
- End date of the study fixed to December 31st, 2019 or to December 31st, 2020 for sensitivity analyses;

- Date of the last reimbursement of care recorded in the SNDS (patients with no consumption or reimbursement of care in the 12 months following the date of last consumption).

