End date of unexposed sequence	
Date variable
 
The end date of unexposed sequence is defined as:
 
 – The day before the Start date of treatment sequence if the patient starts an OAC 
OR
 
 – End of follow-up period in other cases

Second, each event of interest with the occurred dates available in the data extraction for the AF patients in France during their follow-up will be derived by treatment exposure sequence as indicated in [Table VIII](#).

Table VIII. Derived variables for identifying events of interest

Variable	Definition
Stroke (ischemic or hemorrhagic)	
Binary variable (Yes / No)
 
Equals to “Yes” if the patient is hospitalized with any discharge diagnosis (i.e., main, related or associated diagnosis) of stroke (ischemic or haemorrhagic)

	
ICD-10 codes: I60.x, I61.x, I62.9, I63.x, I64.x, G45.x, G46.x, G81.x, S06.4, S06.5, S06.6
 
Equals to “No” in other cases

Major bleeding	
Binary variable (Yes / No)
 
Equals to “Yes” if the patient is hospitalized with any discharge diagnosis (i.e., main, related or associated diagnosis) of major bleeding
 
ICD-10 codes: I60.x, I61.x, I62.9, S06.4, S06.5, S06.6, I85.0, K22.6, K25.0, K25.2, K25.4, K25.6, K26.0, K26.2, K26.4, K26.6, K27.0, K27.2, K27.4, K27.6, K28.0, K28.2, K28.4, K28.6, K29.0, K62.5, K92.0, K92.1, K92.2, D62, H35.6, H43.1 H45.0, H92.2, I31.2, J94.2, R04.x, K66.1, M25.0, N02, N93.8, N93.9, N95.0, R31, R58, T79.2
 
Equals to “No” in other cases

Death	
Binary variable (Yes / No)
 
Equals to “Yes” if the date of death is reported in DCIR
 
Equals to “No” in other cases

Date of occurrence	
Date variable
 
Equals to the value of date when occurred the event

In the case of a patient presents an event of interest during the grace period, which ends after the end of the study, the event will be considered neither in an exposed nor in an unexposed period, and the patient will be censured at the end of the study period.

Then, the variable presented in [Table IX](#)[Table X](#) will be derived for the analyses of incidence, for each patient, for each event of interest and for each exposure treatment sequence.

Table IX. Derived variables for the analyses of incidence rate on events of interest

Variable	Definition

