Number of occurrences	
Continuous variable
 
Equals to the number of occurrences where the two criteria are met:
 
 – The variable of the specified event of interest (Stroke, Major bleeding or Death) equals “Yes” – The value of the variable Date of occurrence falls in the specific OAC treatment sequence period for exposed patient and during unexposed sequence period for unexposed patient 
In

And finally, the following variables in [Table X](#) will be derived for all patients selected in the study population.

Table X. Derived variables for study population

Variable	Definition
Incident AF patient	
Binary variable (Yes / No)
 
Equals to “Yes” if:
 
 – The patient is newly diagnosed AF during the inclusion period (i.e. no AF diagnostic during the historical period) 
AND
 
 – No reported events of interest (stroke, major bleeding, and death) between the inclusion date and the first date of OAC delivery among AF patients with at least one dispensation of OAC identified within 30 days from inclusion date (cf. 9.2.3.1. Inclusion Criteria) 
Equals to “No” in other cases
 
Sensitivity analyses on incidence rate of stroke, major bleeding and death, and comparison of these events in regression analyzes will be performed on all newly diagnosed AF during the inclusion period (i.e. no exclusion of patients with reported events of interest between inclusion date and index date among those with at least one dispensation of OAC identified within 30 days from inclusion date).

Gender	
Binary variable (Female / Male)
 
See Table IIIError! Reference source not found.

Age	
Categorical variable (<65 years old / 65-74 / 75-79 / ≥80 years old)
 
See Table III

Death	
Binary variable (Yes / No)
 
See Table III

Lost to follow-up	
Binary variable (Yes / No)
 
Equal to “Yes” if the patient has no consumption or reimbursement of care in the 12 months following the date of last consumption
 
Equals to “No” in other cases

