9.7.4.2 Comparison of the incidence of stroke, major bleeding, death

Analyses will be performed independently for each event of interest stroke, major bleeding and death.

Survival analysis will be performed to compare incidence rate (stroke, major bleeding or death) in AF incident patients exposed and unexposed to OAC therapy **excluding those with a reported outcomes of interest up to 30 days prior index date**, using a Cox regression model. The Cox regressions models will consider the first event of interest occurring in AF incident patients exposed and unexposed to OAC. OAC exposure will be considered as time-dependent variable and the models will be adjusted for covariates defined below. By applying the OAC exposure variable as a time dependent variable, estimates of Hazard Ratio will account for switches and discontinuations. Time-dependent exposure Cox proportional hazards models will be used to estimate:

- The Crude hazard ratio (i.e. the incidence rate ratio), and therefore the risk of each outcome at any point during the follow-up since index date
- The adjusted hazard ratio on potential confounders including patient:
 - Time-fixed confounders: sex, age (<80, 80-90, >90 years old), prescriber's specialty at initiation of OAC, having malnutrition (yes/no), risk of falls (yes/no), morbid obesity (yes/no), history of stroke (yes/no), history of major bleeding (yes/no), at least one visit to a nursing home (yes/no), history of dementia (yes/no), concomitant treatments (e.g. receiving at least one antiplatelet drugs (yes/no), other anticoagulant drugs (yes/no), etc. - cf. *Table XV for all confounders*)
 - Time-dependent confounders: AOC treatment exposure

In a first model, patient exposure will be modelled according to five categories: exposure to apixaban, dabigatran or rivaroxaban, exposure to VKA or unexposed patients. In a second model, exposure to DOACs will be integrated instead of exposure to apixaban, dabigatran or rivaroxaban. For both models, the reference for comparison will be VKA exposure.

Same models will be performed on AF incident patients with a high thromboembolic risk (if modified CHAD₂DS₂VASC score is ≥ 2 for males and ≥ 3 females). Patient exposure will be modelled according to three categories: exposure to DOAC (Apixaban, Dabigatran or Rivaroxaban), exposure to VKA or unexposed patients. The reference for comparison will also be VKA exposure.

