Death	xx.x (xx.x)	xx.x (xx.x)	xx.x (xx.x)
Lost to follow-up	xx.x (xx.x)	xx.x (xx.x)	xx.x (xx.x)
End of study period	xx.x (xx.x)	xx.x (xx.x)	xx.x (xx.x)
Duration of the follow-up in years			
Mean (std)	xx.x (xx.x)	xx.x (xx.x)	xx.x (xx.x)
Median	xx.x	xx.x	xx.x
Q1 - Q3	xx.x - xx.x	xx.x - xx.x	xx.x - xx.x
Min - Max	xx.x - xx.x	xx.x - xx.x	xx.x - xx.x
Duration group of the follow-up in years: n (%)			
[0-1[xx.x (xx.x)	xx.x (xx.x)	xx.x (xx.x)
[1-2[xx.x (xx.x)	xx.x (xx.x)	xx.x (xx.x)
[2-3[xx.x (xx.x)	xx.x (xx.x)	xx.x (xx.x)
[3-4[xx.x (xx.x)	xx.x (xx.x)	xx.x (xx.x)
[4-5]*	xx.x (xx.x)	xx.x (xx.x)	xx.x (xx.x)

*This category will be display only for the sensitivity analysis (up to 2020)

2. Shell Tables and Figures of Results of the Planned Analysis for the Primary Objective

Table A2. Incidence rate for stroke, major bleeding and death in AF incidents patients between 2016 and 2019 in France – <POPULATION>

<POPULATION>	Stroke				Major bleeding				Death			
	n	N	Crude	Standardized **	n	N	Crude	Standardized %**	n	N	Crude	Standardized **
Overall	x	x	x,x [x,x;x,x]	NA	x	x	x,x [x,x;x,x]	NA	x	x	x,x [x,x;x,x]	NA
CI 95%				NA				NA				NA
Unexposed to OAC*	x	x	x,x [x,x;x,x]	x,x [x,x;x,x]	x	x	x,x [x,x;x,x]	x,x [x,x;x,x]	x	x	x,x [x,x;x,x]	x,x [x,x;x,x]
CI 95%												
Exposed to OAC	x	x	x,x [x,x;x,x]	NA	x	x	x,x [x,x;x,x]	NA	x	x	x,x [x,x;x,x]	NA
CI 95%				NA				NA				NA
VKAs	x	x	x,x [x,x;x,x]	NA	x	x	x,x [x,x;x,x]	NA	x	x	x,x [x,x;x,x]	NA
CI 95%				NA				NA				NA
DOACs	x	x	x,x [x,x;x,x]	NA	x	x	x,x [x,x;x,x]	NA	x	x	x,x [x,x;x,x]	NA
CI 95%				NA				NA				NA
Apixaban	x	x	x,x [x,x;x,x]	NA	x	x	x,x [x,x;x,x]	NA	x	x	x,x [x,x;x,x]	NA
CI 95%				NA				NA				NA
Dabigatran	x	x	x,x [x,x;x,x]	NA	x	x	x,x [x,x;x,x]	NA	x	x	x,x [x,x;x,x]	NA
CI 95%				NA				NA				NA
Rivaroxaban	x	x	x,x [x,x;x,x]	NA	x	x	x,x [x,x;x,x]	NA	x	x	x,x [x,x;x,x]	NA
CI 95%				NA				NA				NA

OAC: Oral anticoagulant; DOACs: Direct oral anticoagulants; VKAs: Antivitamins K; NA, not applicable.

n: number of events of interest; N: number of person-years of follow-up

*Unexposed and exposed to OAC correspond to the period of time where the patients are not exposed to OAC and exposed to OAC, respectively

%: Incidence of the event of interest; CI 95%: 95% confidence interval

**: Standardized on age group (<65 years old; 65-74 years old; 75-79 years old; ≥80 years old) using the exposed population as reference

<POPULATION>: Incidence rate of events will be stratified in the following sub-groups:

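### The primary stroke and major-bleeding rates count first events but divide by all follow-up, including time after the event, so as written they are too low

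*SAP*

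**What the plan says.** Numerator, SAP 9.7.3.1: "The analysis of incidence rate for the first occurrence of each event of interest". The formula sentence later in that section speaks only of events during follow-up, as does protocol 3.7.1, which has no first-event limit.

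Denominator, same section: "divided by the number of person-years of follow-up (sum of durations of follow-up period for incident patients".

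End of follow-up, SAP 9.2.1.4: "The Follow-up period starts at index date and ends on the date of occurrence of one of the following events". The list that follows is death, the end of the study, and the last recorded reimbursement. Stroke and bleeding are not on it.

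Exposure sequences, SAP 9.4.2, Table VII: a treatment sequence ends at a switch, or 30 days after the last delivery when no OAC is reimbursed in the next 60 days. An unexposed sequence ends at an OAC start or, failing that, "End of follow-up period in other cases".

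Event count, SAP 9.4.2, Table IX: "Equals to the number of occurrences where the two criteria are met". The criteria are that the event is present and its date falls in the sequence. The count is not limited to the first.

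Shell Tables A2 and A3, footnotes: "n: number of events of interest; N: number of person-years of follow-up".

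Secondary comparison, SAP 9.7.4.2: "The Cox regressions models will consider the first event of interest occurring in AF incident patients exposed and unexposed to OAC".

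**The concern.** A first-event rate needs a denominator made of time during which a first event can still happen. Here the denominator also holds the time from each patient's first stroke or bleed to the end of follow-up. That time can add nothing to the numerator, so it can only lower the overall rate.

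This formula defines two of the three outcomes of the primary objective, overall and in every subgroup. The error grows with the event rate, so it is largest in high-risk subgroups.

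Person-time is split by current exposure, so post-event time is credited to whichever state the patient moves into. A patient who stops an OAC after a bleed adds person-time without a possible first event to the unexposed denominator. The descriptive contrast between exposed and unexposed can then move even when there is no OAC effect. The primary rates would also not match the first-event Cox results printed in the same report.

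**Working it through.** **No stated figure to reproduce.** Neither document gives a stroke, bleeding, death or switching rate, so the size has to be shown under assumptions.

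**Set-up (assumed).** Constant hazards: first event λ, death μ. Potential follow-up is uniform on 0 to T = 4 years, which corresponds to steady entry over 2016-2019 and a stop at the end of 2019. Let P be mean time before the first event and Q mean time after it. Then

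- correct rate = λP / P = λ
- rate as written = λP / (P + Q)

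Write g(h) = [T − (1 − e^(−hT))/h] / (hT). Then P = g(λ + μ). If death is no more frequent after the event, P + Q = g(μ).

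**Example: λ = 0.04, μ = 0.08.**

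- P = g(0.12) = (4 − 3.177)/0.48 = 1.715 years
- P + Q = g(0.08) = (4 − 3.423)/0.32 = 1.803 years
- Rate as written = 4 × 1.715/1.803 = 3.81 per 100 person-years (PY), which is 4.9% too low

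**Range.** Death 5, 8 or 12 per 100 PY; death after the event 1 or 3 times as high (numerical integration):

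| True first-event rate per 100 PY | Error as written |
|---|---|
| 1 | −1.0 to −1.3% |
| 4 | −3.9 to −5.0% |
| 8 | −7.5 to −9.6% |
| 10 | −9.2 to −11.7% |

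A separate calculation with mortality of 0 or 10 per 100 PY before the event, and 0, 10 or 30 after it, gave −1.0 to −1.3% at 1 per 100 PY, −5.0 to −6.3% at 5, and −9.6 to −12.1% at 10.

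**Against sampling error.** SAP 9.5 cites 225,747 new OAC users in 2018. Over four inclusion years, 225,747 × 4 = 902,988 patients. Then 902,988 × 1.803 = 1.63 million PY, and 1.63 million × 3.81/100 ≈ 62,000 first strokes. The relative 95% CI half-width is 1.96/√62,000 = 0.8%, so the 4.9% error is about six times larger and the interval would exclude the true rate. At 1 per 100 PY the error (about 1.3%) and the half-width (about 1.5%) are similar.

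**Shift between exposure groups.** Let e and u mark exposed and unexposed person-time, each weighted by its share of patients.

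- Exposed N = Pe + Qe(1 − stop) + Qu × start
- Unexposed N = Pu + Qu(1 − start) + Qe × stop

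Bleeding example with no OAC effect: λ = 0.08, μ = 0.08, 75% exposed, 50% stopping after a bleed, none starting. P = g(0.16) = 1.634 and Q = 1.803 − 1.634 = 0.169, so Pe = 1.225, Qe = 0.127, Pu = 0.408, Qu = 0.042.

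- Exposed: 8 × 1.225/(1.225 + 0.063) = 7.61
- Unexposed: 8 × 0.408/(0.408 + 0.042 + 0.063) = 6.36
- Ratio 1.20, where the truth is 1.00

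Other cases, all with a true ratio of 1.00, death 8 per 100 PY and 60-75% exposed:

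| Outcome and true rate | Stop OAC after event | Start OAC after event | Ratio as written |
|---|---|---|---|
| Stroke, 4 per 100 PY | 0-30% | 50-80% | 0.94-1.03 |
| Bleeding, 8 per 100 PY | 30-50% | 0-20% | 1.03-1.20 |
| Bleeding, 8 per 100 PY | 10% | 20% | 0.99-1.01 |
| Bleeding, 4 per 100 PY | 30-50% | 0-20% | 1.02-1.10 |
| Bleeding, 2 per 100 PY | 30-50% | 0-20% | 1.01-1.05 |

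**Table IX reading.** If every coded stay counts, and stroke patients have 0.2 to 0.5 extra coded stays each (assumed), the 3.81 becomes 3.81 × 1.2 = 4.6 to 3.81 × 1.5 = 5.7 per 100 PY from the same data.

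**The case against.** The strongest reply is that the SAP may intend all events. Only the opening of 9.7.3.1 says first; the formula sentence, protocol 3.7.1, Table IX and the shell footnotes do not. With all events counted, full follow-up is a coherent denominator and the rate is not biased downward. This stands as a description of the conflict, but it does not rescue the plan. It contradicts the stated first-occurrence analysis and gives a recurrent-event rate. It also needs a rule to tell a new stroke from a repeat stay coded for the same one: Table VIII accepts any main, related or associated diagnosis, and no such rule is given. Either reading needs a text change.

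A second reply is that outcome-specific person-time was probably meant. Table A2 prints a separate N for each outcome, SAP 9.4.2 has a censoring sentence for events in a grace period running past study end, and 9.7.4.2 equates the crude hazard ratio with the incidence rate ratio. These suggest the right intention, but the explicit denominator in 9.7.3.1 says otherwise, and SAP 9.6 has the statistician follow the signed-off text. Two design figures (SAP Appendix 1, protocol Figure 2) could not be read in the text available; a figure could clarify intent but would still conflict with the written formula.

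Third, the primary analysis is descriptive, the Cox comparison is unaffected, and the error is small at low rates. All of that is true. The ratio of 1.20 is the extreme of the cases tried, and exceeding sampling error in a cohort of about 900,000 does not by itself make an error important in practice.

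**Conclusion.** The concern holds. Under the first-occurrence wording of SAP 9.7.3.1, the direction is certain for the overall stroke and major-bleeding rates: they are too low. Death is not affected, and neither is the Cox analysis.

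The size rests on assumed constant hazards, follow-up uniform over 0-4 years and assumed mortality: roughly 1% at 1 per 100 PY, 4-5% at 4, and 7.5-10% at 8. The effect on the exposed/unexposed contrast has no fixed direction. For stroke it can be nil or go either way. For bleeding it tends to lower the unexposed rate if patients stop their OAC after a bleed.

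Because this is the definition of two of the three primary outcomes, and Table IX contradicts it, it must be settled before the primary tables are programmed.

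**What to change.** If first events are intended:

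- In SAP 9.7.3.1, for stroke and for major bleeding separately, run person-time from the index date to the earliest of first event of that type, death, last reimbursement or study end. Allocate it to exposure sequences up to that date only.
- In Table IX, replace the count of occurrences with a 0/1 flag for the first event.
- In Tables A2 and A3, define N as outcome-specific person-years at risk. For Table A3, state whether time stops at the first stroke of either type or at the first of the type reported.

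If all occurrences are intended, remove the first-occurrence wording, define what separates a new event from a repeat stay, and report a recurrent-event rate over full follow-up with a variance that allows for within-patient correlation.

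The cost of the first option is wording in 9.7.3.1, Table IX and two footnotes. The shells already have a separate N for each outcome, and the first-event Cox models already need these event times.
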